**Purpose:**

As noted in protocol version 3.0 dated 05 January 2017, skin punch biopsies of the thigh and leg for evaluation of intraepidermal nerve fiber density (IENFD) and sweat gland nerve fiber density (SGNFD) will be collected at the 52 Week visit, and annually thereafter. The samples have been and are being quantified through stereologic evaluation of the immunostained nerve fibers.

This letter is to clarify that skin punch biopsies collected under this protocol will also be stained for amyloid to determine amyloid burden. Characterization of amyloid burden will serve as an additional exploratory assessment. Amyloid burden assessment will be performed on all collected skin punch biopsies by the same laboratory performing the IENFD and SGNFD assessments.

As the study-specific informed consent form (ICF) does not describe the specific analyses being performed on these biopsies, and as such, the ICF does not require any updating.

The changes in the protocol are specified below; added text is indicated by **bold** font:

**Section 8.1.3: Intraepidermal Nerve Fiber Density and Sweat Gland Nerve Fiber Density, Page 37**

For patients who had skin biopsies on the parent study and who have provided additional voluntary consent for skin biopsy on this study, 2 sets of tandem 3-mm skin punch biopsies (4 biopsies total) for IENFD and SGNFD **and amyloid burden characterization** will be obtained at each time point.

PPD

02 May 2017

\_\_\_\_\_  
Date

### Version History:

Version Number	Date	Comment
1.0 (Original)	06 November 2014	Initial Release
2.0 – Global	08 September 2015	Incorporating Global Amendment 1
2.1 – Japan	14 October 2015	Incorporating Japan-specific Amendment 1
2.1 – Taiwan	10 December 2015	Incorporating Taiwan-specific Amendment 1
2.1 – France/Germany	17 December 2015	Incorporating France/Germany-specific Amendment 1
2.2 – Japan	14 March 2016	Incorporating Japan-specific Amendment 2
3.0 - Global	05 January 2017	Incorporating Global Amendment 2 (including Japan-, Taiwan- and France/Germany-specific changes)

## SYNOPSIS

Name of Sponsor/Company: Alnylam Pharmaceuticals, Inc
Name of Investigational Product: Patisiran
Title of Study: A Multicenter, Open-Label, Extension Study to Evaluate the Long-term Safety and Efficacy of Patisiran in Patients with Familial Amyloidotic Polyneuropathy Who Have Completed a Prior Clinical Study with Patisiran
Study Centers: This study will be conducted at multiple sites worldwide that have enrolled patients in a previous patisiran study.
Objectives: To assess the safety and efficacy of long-term dosing with patisiran in transthyretin-mediated amyloidosis (ATTR) patients with familial amyloidotic polyneuropathy (FAP).
Methodology: This is a multicenter, multinational, open-label extension study to evaluate the long-term safety and efficacy of patisiran in patients with FAP who have previously completed a patisiran study. Consented eligible patients will enroll in this study and receive 0.3 mg/kg patisiran intravenously (IV) once every 21 ( $\pm$ 3) days for the duration of the study. In order to maintain the every 21-day dosing schedule from the parent study, patients are expected to have their first visit (Day 0) in this study 3 weeks after their last dose visit in the parent study. However, if necessary, a patient may initiate dosing in this study up to 45 days from the time of the last dose in the parent study. Exceptions to this timing may be allowed for medical or regulatory considerations only after consultation with the Medical Monitor. The last testing visit in the parent study will serve as the baseline for this study, unless more than 45 days have elapsed, in which case the baseline tests will need to be repeated on Day 0. Eligibility for this study will be confirmed before administration of the first dose on Day 0. After the Day 0 visit, patients should return to the site for patisiran dosing once every 21 days. Where applicable country and local regulations allow, patients may receive the patisiran infusions at home by a healthcare professional trained on the protocol and delivery of premedications and patisiran. Patients who are receiving patisiran infusions at home will have a phone contact with the site at least every 30 ( $\pm$ 5) days. Patients will also have visits at the clinical site at approximately 12, 26 and 52 weeks, and yearly thereafter. A complete set of efficacy assessments will be done at 52 weeks, followed by more limited efficacy assessments yearly thereafter. In order to decrease the variability in the efficacy assessment testing at the 52-week visit, there will be a limited number of sites within any one territory that conduct these efficacy assessments (referred to as “Central Assessment Sites [CAS]”); these sites can also dose and manage patients. There will also be sites that can dose and manage the patients (“Patient Care Sites [PCS]”), while sending the patients to the nearest CAS for their 52-week efficacy assessments. Every effort should be made for the patient to return to the same CAS center that the patient went to in the parent study. Yearly efficacy assessments after the 52-week visit may be done at a PCS. Safety will be assessed throughout the study. Patients will return to the clinical site for safety evaluations 12, 26 and 52 weeks during the first year and yearly thereafter. Patients will be continually assessed throughout the study for adverse events (AEs). Unscheduled visits for study assessments may

occur if deemed necessary by the study personnel.

**Number of patients (planned):**

All patients who have previously completed a patisiran study may be enrolled if they meet the eligibility criteria for this study.

**Diagnosis and eligibility criteria:**

To be enrolled in the study, patients must meet the following criteria before administration of patisiran on Day 0:

1. Have completed a patisiran study (ie, completed the last efficacy visit in the parent study) and, in the opinion of the investigator, tolerated study drug
2. Be considered fit for the study by the Investigator
3. Have aspartate transaminase (AST) and alanine transaminase (ALT) levels  $\leq 2.5 \times$  the upper limit of normal (ULN), international normalized ratio (INR)  $\leq 2.0$  (patients on anticoagulant therapy with an INR of  $\leq 3.5$  will be allowed)
4. Have a total bilirubin within normal limits. A patient with total bilirubin  $\leq 2 \times$  ULN is eligible if the elevation is secondary to documented Gilbert's syndrome (elevation of unconjugated bilirubin with normal conjugated bilirubin) and the patient has ALT and AST levels within normal ranges.
5. Have a serum creatinine  $\leq 2 \times$  ULN
6. Women of child-bearing potential must have a negative pregnancy test, cannot be breastfeeding, and must be using 2 highly effective methods of contraception prior to dosing in this study and agree to use 2 highly effective methods of contraception throughout study participation and for 75 days after last dose of patisiran in this study.
7. Males with partners of child-bearing potential must agree to use 1 barrier method (eg, condom) and 1 additional method (eg, spermicide) of contraception throughout study participation and for 75 days after the last dose of patisiran in this study; males must also abstain from sperm donation after the first dose of patisiran through study participation and for 75 days after last dose of patisiran in this study
8. Be willing and able to comply with the protocol-required visit schedule and visit requirements and provide written informed consent

A patient will be excluded if they meet any of the following criteria before dosing on Day 0:

1. Has an active infection requiring systemic antiviral or antimicrobial therapy that will not be completed before the first dose of patisiran administration
2. Has poorly controlled diabetes mellitus
3. Has uncontrolled cardiac arrhythmia or unstable angina
4. Is currently taking tafamidis, diflunisal, doxycycline, or tauroursodeoxycholic acid (TUDCA), unless previously allowed per the parent study
5. Is unable to take the required premedications, unless modifications to the premedication regimen were previously allowed per the parent study
6. Is under legal protection (defined as "any person who becomes incapable of protecting his/her interests due to a medically diagnosed impairment of his/her mental faculties that may limit or prevent the expression of his will"), decided by a court

**Investigational product, dosage and mode of administration:**

Patisiran (comprising a small interfering ribonucleic acid [siRNA] targeting mutant and wild type transthyretin [TTR] messenger RNA [mRNA], in a lipid nanoparticle formulation for IV administration), 0.3 mg/kg once every 21 ( $\pm$ 3) days administered as an IV infusion over 70 minutes (approximately 1 mL/minute for the first 15 minutes followed by approximately 3 mL/minute for the remainder of the infusion) by a controlled infusion device.

Patients will receive the following premedications at least 60 minutes before the start of the patisiran infusion:

- Intravenous dexamethasone (10 mg) or equivalent
- Oral paracetamol/acetaminophen (500 mg) or equivalent
- Intravenous H2 blocker (ranitidine 50 mg, famotidine 20 mg, or equivalent other H2 blocker dose)
- Intravenous H1 blocker: diphenhydramine 50 mg (or equivalent other IV H1 blocker available at the study site). Hydroxyzine 25 mg per os (PO, orally) or fexofenadine 30 mg or 60 mg PO or cetirizine 10 mg PO may be substituted for any patient who does not tolerate IV diphenhydramine or other IV H1 blocker.

**Duration of treatment:**

The duration of the study has been determined to allow the collection of long-term safety, tolerability and efficacy data of patisiran in patients with FAP who have completed a prior study with patisiran. The estimated duration of the study is 5 years.

**Reference therapy, dosage and mode of administration:**

Not applicable.

**Criteria for evaluation:**

**Efficacy:**

The efficacy of patisiran will be assessed by the following evaluations:

- Neurological impairment assessed using the Neuropathy Impairment Score (NIS), Modified NIS (mNIS +7) composite score, and NIS+7
- Patient-reported quality of life (QOL) using the Norfolk Quality of Life-Diabetic Neuropathy (QOL-DN) and the EuroQOL (EQ-5D) questionnaires
- Disability reported by patients using the Rasch-built Overall Disability Scale (R-ODS)
- Autonomic symptoms assessed using the Composite Autonomic Symptom Score (COMPASS 31)
- Motor function assessments, including NIS-Weakness (NIS-W), timed 10-meter walk test, and grip strength test
- Polyneuropathy disability (PND) score and FAP stage
- Nutritional status using modified body mass index (mBMI)
- Pathologic evaluation of sensory and autonomic innervation evaluated by intraepidermal nerve fiber density (IENFD) analysis and quantitation of dermal sweat gland nerve fibers (SGNFD) via tandem 3 mm skin punch biopsies taken from the leg (only for patients having this assessment in the parent study)
- Magnetic resonance (MR) neurography (as regionally applicable)
- Cardiac structure and function through echocardiograms and serum levels of terminal

prohormone of B-type natriuretic peptide (NT-proBNP) and troponin I

- New York Heart Association (NYHA) classification of heart failure
- Serum TTR
- Vitamin A
- Thyroid stimulating hormone
- Disease burden and healthcare utilization assessed using a patient-reported pharmacoeconomics questionnaire

**Safety:**

Safety assessments will include monitoring for AEs (including serious AEs [SAEs]); clinical laboratory tests, including hematology, clinical chemistry, urinalysis, and pregnancy testing; measurement of anti-drug antibodies (if clinically indicated); vital signs; physical examinations; ophthalmology examinations; and assessment of suicidal ideation and behavior.

**Statistical methods:**

This is an open-label extension study enrolling patients who have previously completed a patisiran study; the size of the study is not determined via power analysis of particular hypotheses tests.

Associations between pharmacodynamic and efficacy data will be explored via correlation.

Descriptive statistics will be provided for clinical efficacy data, clinical laboratory data, vital signs data, and ECG interval data, presented as both actual values and changes from baseline relative to each on-study evaluation. Laboratory shift tables from baseline to worst values will be presented.

**Table 1 Schedule of Assessments**

	Day 0 Visit	12 Week Visit	26 Week Visit	52 Week Visit	Annual Visit	End of Study	Early Withdrawal Visit
	Window ≤45 Days from Last Dose a	±4 Weeks	±4 Weeks	±4 Weeks	±6 Weeks	4 (+1) Weeks from Last Dose	4 (+1) Weeks from Last Dose
Procedure							
Informed Consent	X						
Inclusion/Exclusion Criteria	X						
Medical History	X b						
Demographics	X c						
Physical Examination	X d			X	X	X o	X o
Weight	X Prior to Each Dose					X o	X o
mBMI e	X d			X	X	X o	X o
Height	X c						
FAP Stage and PND Score	X d			X	X	X o	X o
Karnofsky Performance Status	X						
NYHA Classification	X			X			[X] f
Vital Signs g	X Prior to Each Dose						
Safety Laboratory Assessments h	X d	X	X	X	X	X	X
INR	X						
Pregnancy Test (urine)	X i		X	X	X	X	X
C-SSRS Questionnaire			X	X	X	X	X

	Day 0 Visit	12 Week Visit	26 Week Visit	52 Week Visit	Annual Visit	End of Study	Early Withdrawal Visit
	Window ≤45 Days from Last Dose a	±4 Weeks	±4 Weeks	±4 Weeks	±6 Weeks	4 (+1) Weeks from Last Dose	4 (+1) Weeks from Last Dose
Procedure							
TTR Protein (ELISA)	X d		X	X	X	X	X
TSH and Vitamin A				X	X	X o	X o
Blood Sample for Long-term Storage	X	X	X	X	X	X	X
mNIS+7 j	X d			X			[X] f
NIS+7 k	X d			X			[X] f
NIS only					X l	X m	X m
Grip Strength Test n	X d			X			[X] f
10-Meter Walk Test p	X d			X			[X] f
Ophthalmology Examination q	X d			X	X	X o	X o
Skin Punch Biopsy (IENFD and SGNFD) r				X	X	X o	X o
MR Neurography s ( Germany & France only )	X		X	X	X	X o	X o
Pharmacoeconomics Questionnaire	X			X	X	X o	X o
Norfolk QOL-DN t	X d			X	X	X o	X o
COMPASS 31 Questionnaire	X d			X			[X] f
R-ODS Disability	X d			X			[X] f
EQ-5D QOL	X d			X	X	X o	X o
Echocardiogram	X d,u			X			[X] f
Troponin I and NT-proBNP	X d			X			[X] f
Anti-Drug Antibody Testing v			X	X	X	X	X

	Day 0 Visit	12 Week Visit	26 Week Visit	52 Week Visit	Annual Visit	End of Study	Early Withdrawal Visit
Window	≤45 Days from Last Dose a	±4 Weeks	±4 Weeks	±4 Weeks	±6 Weeks	4 (+1) Weeks from Last Dose	4 (+1) Weeks from Last Dose
Procedure							
Premedication / Patisiran Administration w	X		X				
Phone Contact x ( In applicable regions only )			X				
Adverse Events				X b			
Concomitant Medications				X b			

**Table 1 Footnotes:**

Abbreviations: C-SSRS = Columbia-Suicide Severity Rating Scale; COMPASS 31 = Composite Autonomic Symptom Score; ELISA = enzyme linked immunosorbent assay; EQ-5D QOL = EuroQOL; FAP = familial amyloidotic polyneuropathy; IENFD = intraepidermal nerve fiber density; mBMI = modified body mass index; mNIS = Modified Neuropathy Impairment Score; MR = magnetic resonance; NIS = Neuropathy Impairment Score; NT-proBNP = N-terminal prohormone of B-type natriuretic peptide; NYHA = New York Heart Association; PND = polyneuropathy disability; QOL-DN = Quality of Life-Diabetic Neuropathy; R-ODS = Rasch-built Overall Disability Scale; SGNFD = sweat gland nerve fiber density; TSH = thyroid stimulating hormone; TTR = transthyretin

- Every effort should be made to perform Day 0 visit 3 weeks (±3 days) from the last dose of study drug in the parent study. However, the Day 0 visit may occur within 45 days after the last dose in the parent study. Exceptions may be made for medical or regulatory considerations only after consultation with the Medical Monitor.
- Medical history includes TTR genotype. Ongoing AEs from the parent study will be captured as Medical History on the case report form (CRF). Similarly concomitant medications that continue from the parent study will be entered into the database.
- Assessment does not need to be repeated. Information will be obtained from parent study.
- Assessment/procedure does not need to be repeated if performed during the parent study within 45 days of first dose in this study.
- mBMI will be calculated within the clinical database; this calculation does not need to be performed at the study center.
- Assessment/procedure required only if patient withdraws before the 52-week visit.
- Vital signs include blood pressure, heart rate, body temperature, and respiratory rate. Collected supine using an automated instrument after patient rests for 10 minutes. Must be performed pre-dose.
- Includes serum chemistry, hematology, and urinalysis. Refer to Section 9.1.5 for specific laboratory assessments.
- Assessment does not need to be repeated if the patient had a negative pregnancy test (urine or serum) within 14 days of the first dose.

- j. The mNIS+7 consists of the modified NIS tool (weakness and reflexes), nerve conduction studies (NCS) 5 attributes ( $\Sigma 5$ ), quantitative sensory testing (QST) by body surface area including touch pressure (TP) and heat pain (HP), and postural blood pressure. Two assessments of the mNIS+7 will be performed on separate days (1 assessment on each day). The second (repeat) assessment must be conducted at least 24 hours (approximately) but not more than 7 days after the first assessment. Each site will make every effort to have these assessments at the Week 52 visit performed by the same study personnel who performed the assessments for the patient in the patisiran study in which they were previously enrolled.
- k. The NIS+7 consists of the NIS tool (weakness, sensation, and reflexes), NCS  $\Sigma 5$ , vibration detection threshold (VDT), and heart rate response to deep breathing (HRdB). Two assessments of the NIS+7 will be performed on separate days (1 assessment on each day). The second (repeat) assessment must be conducted at least 24 hours (approximately) but not more than 7 days after the first assessment. Each site will make every effort to have these assessments at the Week 52 visit performed by the same study personnel who performed the assessments for the patient in the patisiran study in which they were previously enrolled.
- l. One assessment of the NIS will be performed at each specified visit and must be performed by a neurologist.
- m. Assessment of NIS only does not need to be repeated if done as part of the NIS+7 at the End of Study or Early Withdrawal visit or if done within the previous 26 weeks.
- n. Grip strength will be measured in triplicate using a dynamometer held in the dominant hand. Every effort will be made to use the same device for a patient throughout the duration of the study. Two assessments of the grip strength will be performed on separate days (1 assessment on each day). The second (repeat) assessment must be conducted at least 24 hours (approximately) after the first assessment, but not more than 7 days apart.
- o. Assessment does not need to be repeated if done within the previous 26 weeks.
- p. The patient will be asked to walk 10 meters. The walk must be completed without assistance from another person; ambulatory aids such as canes and walkers are permitted. The time required for the patient to walk 10 meters will be recorded. Two assessments of the 10-meter walk test will be performed on separate days (1 assessment on each day). The second (repeat) assessment must be conducted at least 24 hours (approximately) but not more than 7 days after the first assessment.
- q. Examination will include visual acuity, visual fields, and slit-lamp evaluation. An electroretinogram may also be performed, as described in Section 9.1.6
- r. Optional skin biopsies will only be obtained if the patient had skin biopsies in the parent study and has provided separate informed consent for the skin biopsies in this study. Each skin biopsy assessment will include 2 sets of tandem 3-mm skin punch biopsies (4 biopsies total), including 1 set of biopsies taken from the distal lower leg, when a patient's clinical status allows, and 1 set from the distal thigh.
- s. MR neurography will only be conducted at sites in Germany and France. In these countries, neurography may be conducted for patients who had MR neurography in the parent study and for a subset of patients providing informed consent who did not have MR neurography previously in their parent study. Patients who had imaging in the parent study should have Day 0 imaging if they did not undergo MR neurography within the past 3 months.
- t. Patients who are entering this study from a protocol that does not include the Norfolk QOL-DN questionnaire (eg, ALN-TTR02-003) do not have to complete this assessment.
- u. Patients entering this study from study ALN-TTR02-003, who were not previously participating in the cardiac subgroup, will be required to have an echocardiogram before dosing on Day 0.
- v. Serum samples for anti-drug antibodies will be collected as specified.
- w. Patisiran will be administered once every 21 ( $\pm 3$ ) days. Every effort should be made to continue dosing from the parent study in the 21 ( $\pm 3$ ) day timeframe. Doses may be administered at the clinical site or, where applicable country and local regulations allow, at home by a healthcare professional trained in the protocol.
- x. Patients who are receiving patisiran infusions at home must be contacted by the clinical site a minimum of every 30 ( $\pm 5$ ) days for assessment of adverse events and concomitant medication use. During phone contact, patients may also be asked additional questions about their general experience receiving infusions at home.

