### 4.3. Patient Withdrawal Criteria

Patients are free to withdraw from the study at any time and for any reason, without penalty to their continuing medical care. For those patients who withdraw, every effort will be made to determine their reason for dropping out, and to complete the Early Withdrawal visit.

The Investigator may withdraw a patient from the study if the patient:

- Is in violation of the protocol
- Experiences a serious or intolerable AE
- Becomes pregnant
- Requires a prohibited medication (see Section 5.2)
- Requests to be withdrawn from the study
- Is found to be considerably noncompliant with the protocol-required patisiran dosing visits

The Investigator will withdraw patients from the study upon the request of the Sponsor, including if the Sponsor terminates the study. Upon occurrence of a serious or intolerable AE, the Investigator will confer with the Sponsor before discontinuing the patient.

Missing an occasional dose of patisiran will not necessarily result in the patient being withdrawn from the study. However, if a patient misses 3 consecutive doses of patisiran, the Investigator at the clinical site and the Medical Monitor will determine whether the patient should be withdrawn from the study. If the patient is withdrawn from the study, the reason will be noted in the patient medical record and on the case report form (CRF).

In the event a patient is withdrawn from the study, the clinical research organization (CRO) Medical Monitor must be informed immediately.

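### At Early Withdrawal the 26-week waiver can be met by the baseline itself, so early dropouts may leave with no post-baseline PND/FAP stage, EQ-5D or (patients from -004) Norfolk QOL-DN

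*Protocol*

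**What the plan says.** Table 1 (Schedule of Assessments, global version 3.0) places FAP stage and PND score, EQ-5D and Norfolk QOL-DN at Day 0, Week 52 and the annual visits, with nothing at Weeks 12 or 26. The Synopsis describes the plan in the same way: "A complete set of efficacy assessments will be done at 52 weeks, followed by more limited efficacy assessments yearly thereafter".

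Four footnotes decide what is collected from a patient who leaves:

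- **Footnote o** (PND/FAP stage, EQ-5D, Norfolk QOL-DN, mBMI and several other rows, at End of Study and Early Withdrawal): "Assessment does not need to be repeated if done within the previous 26 weeks".
- **Footnote m** (NIS only, at the same two visits) has two clauses. The first is "Assessment of NIS only does not need to be repeated if done as part of the NIS+7 at the End of Study or Early Withdrawal"; the second is "or if done within the previous 26 weeks".
- **Footnote f** (mNIS+7, NIS+7, grip strength, 10-meter walk, COMPASS 31, R-ODS, echocardiogram, cardiac biomarkers and NYHA class, at Early Withdrawal): "Assessment/procedure required only if patient withdraws before the 52-week visit". It has no 26-week exemption.
- **Footnote d** governs the age of the baseline: "Assessment/procedure does not need to be repeated if performed during the parent study within 45 days of first dose in this study".

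The Early Withdrawal visit falls 4 (+1) weeks after the last dose. Section 4.3 says of patients who withdraw that "every effort will be made to determine their reason for dropping out, and to complete the Early Withdrawal visit". Under footnote t and Section 8.1.9, patients from a parent study without the Norfolk questionnaire, such as ALN-TTR02-003, do not complete it here.

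**The concern.** Footnote o does not say that the earlier test must be a follow-up test. A baseline taken in the parent study or on Day 0 satisfies it as written. For someone who leaves in the first months, the waiver then does more than avoid a near-duplicate: it lets the site omit the only post-baseline measurement that patient would have given.

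This fits badly with footnote f in the same column. The protocol asks an early dropout for mNIS+7 and NIS+7, each assessed twice on separate days, and for R-ODS and COMPASS 31. It excuses the same patient from a five-question EQ-5D and from ambulation staging.

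Section 10.2.3 plans descriptive summaries of observed values and changes from baseline. If leaving is linked to decline, omitting the last measurement hides that decline in quality of life and ambulation. Section 9.2.1.1 adds that disease progression is not recorded as an adverse event, so safety reporting does not reliably fill the gap. A statistical analysis plan cannot recover values that were never collected.

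**Working it through.** The protocol gives no figure to reproduce: no sample size, dropout rate or expected missingness. The check is calendar arithmetic on Table 1.

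**Inputs**

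- Waiver length: 26 weeks = 182 days (footnotes o and m).
- Age of the baseline at first dose: 0 to 45 days (footnote d; Section 3.1).
- Early Withdrawal visit: 28 to 35 days after the last dose (Table 1).
- Dosing every 21 days, so dose k falls on day 21 × (k − 1), ignoring the ±3-day window.
- Study length: 5 years = 260 weeks (Synopsis).
- Timing of withdrawal: not stated, so assumed below.

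**1. Who can leave without a post-baseline value?**

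Latest last dose still covered = 182 − age of baseline − visit lag.

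| Baseline age (days) | Visit lag (days) | Latest last-dose day | Week | Doses covered |
|---|---|---|---|---|
| 0 | 28 | 182 − 0 − 28 = 154 | 22.0 | 1–8 (dose 8 on day 147) |
| 0 | 35 | 182 − 0 − 35 = 147 | 21.0 | 1–8 |
| 45 | 28 | 182 − 45 − 28 = 109 | 15.6 | 1–6 (dose 6 on day 105) |
| 45 | 35 | 182 − 45 − 35 = 102 | 14.6 | 1–5 (dose 5 on day 84) |

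The waiver therefore reaches patients whose last dose is up to about Week 14 to 22.

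**2. How large a share of withdrawals is that?**

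Assume first that Early Withdrawal visits are spread uniformly over 260 weeks. A 45-day-old baseline shortens the first window by 45/7 = 6.43 weeks.

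- Share of year-1 withdrawals with no post-baseline value: 26/52 = 50% (Day 0 baseline) or (26 − 6.43)/52 = 38% (45-day-old baseline).
- Share of all withdrawals over 5 years: 26/260 = 10% or 19.57/260 = 8%.
- With a constant hazard of 5%, 10% or 20% per year and a Day 0 baseline, the share of all withdrawals is 11%, 13% or 16%.

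**3. After Week 52**

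Footnote f no longer applies, so the stand-alone NIS is the only neurological impairment score left at Early Withdrawal, and footnote m can waive it.

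- Uniform timing between yearly visits: 26/52 = 50% of these withdrawals may lack a final NIS, PND/FAP stage, EQ-5D and, where applicable, Norfolk value.
- For NIS as a share of all withdrawals: 4 × 26/260 = 40% if uniform; 37–39% at the constant hazards above.
- For the footnote-o outcomes over all 5 years: 5 × 26/260 = 50%, or (19.57 + 104)/260 = 48% with a 45-day-old baseline; 51–53% at the constant hazards.

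Each of these later patients has a Week 52 or annual value at most 26 weeks old.

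**4. Which outcomes are not affected?**

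- *NIS before Week 52.* Footnote f requires NIS+7 at any withdrawal before Week 52, and footnote k states that NIS+7 includes the full NIS. The first clause of footnote m relies on this. The share waived is 0%.
- *mBMI.* Section 8.1.5 derives it in the database as BMI × albumin. Weight is taken before every dose. Albumin is in the chemistry panel, drawn at Weeks 12 and 26 and at Early Withdrawal without a waiver. A post-baseline value can be derived although Table 1 schedules none before Week 52.

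**The case against.** The strongest reply has four parts.

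- *The wording is permissive.* It allows omission and forbids nothing, so a site may still assess. That stands, and it is why the point says patients may lack a value. But a protocol that states a test need not be repeated should expect it to be skipped.
- *The effect on the summaries is not demonstrated.* A value taken between scheduled visits enters a Week 52 or annual summary only if a visit window or missing-data rule places it there. Such rules normally sit in the analysis plan, which is not shown. That also stands: no bias of known size can be claimed, and dropout itself comes first as a source of selection. It does not answer the loss of data, which is settled at collection.
- *The shares are assumed.* They are. The group with no post-baseline value at all is 8–10% of withdrawals under uniform timing.
- *The study is descriptive.* Section 10.1 says its size is not based on power, so no test is compromised. True, but quality of life and ambulation are among the listed efficacy evaluations.

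A reader might also infer that the earliest dropouts lose NIS and mBMI, or that a patient leaving soon after an annual visit has no end-of-participation data at all. The documents do not support this. Footnote f secures NIS in year 1 and mBMI can be derived. At Early Withdrawal, serum TTR, safety laboratory tests and the C-SSRS carry no waiver.

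**Conclusion.** The point holds in a limited form. For PND/FAP stage, EQ-5D and, in patients from ALN-TTR02-004, Norfolk QOL-DN, footnote o as written lets the baseline stand in for follow-up. Patients with a last dose up to about Week 14 to 22 may then contribute no post-baseline value. This follows from Table 1 alone, given the plain reading that a parent-study or Day 0 test counts as done.

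The post-Week 52 gap is weaker. It covers about half of such withdrawals for these outcomes and for NIS under uniform timing, but a recent value exists in each case. Every share rests on assumed withdrawal timing and treats visits as falling exactly on schedule.

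It would go too far to say that the waiver makes years 1 to 5 look more stable by a known amount. The protocol gives neither a dropout rate nor the rule for using Early Withdrawal values. The change is a cheap improvement worth making, not a flaw that invalidates the study.

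**What to change.** Give PND/FAP stage, EQ-5D and Norfolk QOL-DN their own footnote in the Early Withdrawal column: the assessment may be omitted only if it was done after the first dose on this study and within the stated interval. This stops a parent-study or Day 0 baseline from satisfying the waiver and brings these outcomes into line with footnote f.

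Preferably also shorten the 26-week interval for these brief assessments. The documents do not point to a particular length, so the sponsor should choose one and give its reason. NIS needs no change before Week 52; the same shortening could be considered in footnote m for later withdrawals. Keep 26 weeks for skin biopsy, MR neurography and ophthalmology, where burden justifies it. mBMI needs no change.

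Footnote o also covers other rows and the End of Study column, so a separate footnote is cleaner than rewording o. The Argentina version 3.1 carries the same footnotes and needs the same edit. The cost is a few minutes of questionnaires and staging at a visit already planned, plus one neurological examination for some later withdrawals if footnote m is also shortened.
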